#### Narrow Scope

Abdominal discomfort  
Abdominal distension  
Abdominal pain  
Abdominal pain lower  
Abdominal pain upper  
Abdominal symptom  
Abdominal tenderness  
Abnormal faeces  
Aerophagia  
Anorectal discomfort  
Bowel movement irregularity  
Change of bowel habit  
Constipation  
Defaecation urgency  
Diarrhoea  
Epigastric discomfort  
Eruption  
Faecal volume decreased  
Faecal volume increased  
Faeces hard  
Faeces soft  
Flatulence  
Frequent bowel movements  
Gastrointestinal pain  
Gastrointestinal sounds abnormal  
Gastrointestinal toxicity  
Infrequent bowel movements  
Nausea  
Non-cardiac chest pain  
Oesophageal discomfort  
Oesophageal pain  
Premenstrual cramps  
Vomiting

#### Broad Scope

Anorectal swelling  
Antacid therapy  
Antidiarrhoeal supportive care  
Antiemetic supportive care  
Breath odour  
Chest pain  
Colonic lavage  
Dysphagia  
Early satiety  
Gastritis prophylaxis  
Gastrointestinal disorder therapy  
Gastrointestinal tract irritation  
Gastrooesophageal reflux prophylaxis  
Glycogenic acanthosis  
Hypovolaemia  
Laxative supportive care  
Malabsorption  
Mucous stools  
Oesophageal polymer implantation  
Pernicious anaemia  
Post procedural constipation  
Post procedural diarrhea  
Post-tussive vomiting  
Probiotic therapy  
Procedural nausea  
Procedural vomiting  
Prophylaxis against diarrhoea  
Prophylaxis of nausea and vomiting  
Regurgitation  
Retching  
Steatorrhoea  
Vomiting projectile

### 10.6.2 Liver-Related Investigations

The following MedDRA PTs are included in the category “liver-related investigations.”

Alanine aminotransferase abnormal
Alanine aminotransferase increased
Aspartate aminotransferase abnormal
Aspartate aminotransferase increased
Gamma-glutamyl transferase abnormal
Gamma-glutamyl transferase increased
Hepatic enzyme abnormal
Hepatic enzyme increased
Liver function test abnormal
Transaminases abnormal
Transaminases increased

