5.2.4 Summary of Overall Risks and Potential Benefits

Since SA is a normal body compound with native pathways for degradative metabolism and rapid renal clearance, there is no evidence or expectation of a significant safety issue with SA replacement therapy. Data from nonclinical and clinical studies to date suggest SA-ER administered alone or with SA-IR does not pose any significant safety risks that can be identified at this time. Toxicology or adverse pharmacology findings were not observed in SA-treated animals; at very high doses, osmotic diarrhea may be observed in treated dogs.

In the 48-week Phase 2 study in 47 GNEM subjects, there were no deaths or other SAEs. The majority of subjects had TEAEs that were graded as mild to moderate severity. A single subject in the 3 g/day SA-ER group discontinued due to an AE of abnormal liver enzymes; the subject was subsequently identified as having a history of elevated liver function test results. The only AE experienced by a greater proportion of SA-ER treated subjects was abnormal liver function tests (5 subjects vs. 0 in the placebo group). It is likely alanine aminotransferase (ALT) elevations resulted from skeletal muscle disease rather than from liver damage, since gamma-glutamyl transpeptidase (GGT) was generally normal and serum CK was also elevated in these subjects. The time course of abnormality and lack of dose response suggest that these results are not study drug related. Sporadic abnormal levels of aspartate aminotransferase (AST) and ALT were also reported throughout the study, irrespective of time point or treatment group.

The most common treatment-related TEAEs were GI events (diarrhea, flatulence, abdominal pain and dyspepsia), headache and fatigue. The patterns of AEs were similar in the placebo-controlled phase of the study (the first 24 weeks) and for all 48 weeks. No correlation was observed between the GI events and free SA serum levels suggesting the frequency of GI events does not appear to be dose dependent. No subjects from the Placebo group reported diarrhea or abdominal pain, or had abnormal liver function tests after crossing over to SA-ER treatment in the continuation phase of the study.

Safety results in the ongoing Phase 2 study (UX001-CL202) indicate the most common TEAE reported by subjects receiving a higher dose of 12 g/day SA-ER/SA-IR involve GI disorders, including diarrhea, flatulence, dyspepsia, and abdominal pain.

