7.5.6 Appropriateness of Measures

The efficacy parameters to be evaluated in this study include clinical changes in muscle strength, subject mobility and function. The clinical assessments in the study employ standard performance measures used in other neuromuscular diseases and conditions that cause muscle weakness and impaired function. Based on results from Phase 2 studies and published studies ([Aitkens et al. 1989](#)), the study will focus on quantitative muscle testing. The strength of a set of muscle groups in the upper and lower extremities will be assessed by dynamometry, a form of quantitative muscle testing that uses a device with a strain gauge to measure force during a MVIC ([Sisto et al. 2007](#)). An interview-based measure designed to evaluate ability in GNEM patients (GNEM-FAS) will be administered in this study to support the clinical meaningfulness of changes in muscle strength. In addition, walking ability will be assessed using the 6MWT test, a test of endurance commonly used in clinical trials for various indications that has served as the basis for many product approvals.

The level of free SA in serum will reflect the absorption of and exposure of the muscles to SA during treatment. Serum CK level will be assessed as a measure of muscle injury throughout the study; a positive dose-dependent decrease in serum CK levels was observed in the UX001-CL201 Week 24 analysis. Unlike other myopathies, CK activities are mildly elevated or in the normal range for these patients. The mouse model of HIBM showed elevated CK levels that improved substantially on treatment ([Malicdan et al. 2009](#)).

The safety parameters to be evaluated in this study include standard assessments such as recording of medical history, AEs and SAEs, physical examination, neurological examination, vital signs, serum chemistry, and other routine clinical and laboratory procedures. In addition, symptoms of increasing muscle weakness and pain which are characteristic of myopathy will be recorded in interval histories. Suicidal ideation and behavior will be assessed using C-SSRS, a standardized rating instrument recommended in clinical trials of any investigational drug with potential neurological activity (FDA Draft Guidance, 2012).

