#### **8.9.1 Adverse Events to Monitor**

Appendix 10.6 includes certain adverse events and liver related investigations.

Tables summarizing patient incidence of the following will be generated:

- All AEs;
- SAEs;
- Treatment-related AEs;
- Treatment Related SAEs
- Liver-related Investigations

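### The SAP's liver category pools transaminase terms with GGT and omits bilirubin and alkaline phosphatase, and no planned output reads ALT or AST jointly with GGT, bilirubin or CK

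*SAP*

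**What the plan says.** SAP Appendix 10.6.2 introduces its list with "The following MedDRA PTs are included in the category" of liver-related investigations. The list has eleven preferred terms:

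- six for ALT, AST or transaminases, such as "Alanine aminotransferase increased";
- two for GGT, including "Gamma-glutamyl transferase increased";
- three non-specific: hepatic enzyme abnormal, hepatic enzyme increased, and liver function test abnormal.

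There is no bilirubin or alkaline phosphatase term, although both analytes are in the chemistry panel (Protocol Table 7.5.5.6.1). SAP 8.9.1 points to the list ("Appendix 10.6 includes certain adverse events and liver related investigations") and asks for a patient-incidence table of the category. It does not say whether the terms will be shown separately in that table.

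Protocol 5.2.4 reports abnormal liver function tests in Phase 2 as the one adverse event seen in a larger share of SA-ER subjects, 5 against 0 on placebo. Its explanation is a joint reading. The conclusion drawn is: "It is likely alanine aminotransferase (ALT) elevations resulted from skeletal muscle disease rather than from liver damage". The grounds offered are that GGT mostly stayed within normal limits while CK was high in the same people. It also cites the time course and the lack of a dose response.

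SAP 8.9 tabulates treatment-emergent events by system organ class and preferred term. It summarises each laboratory analyte separately, by out-of-range counts, descriptive statistics, and changes or normal/abnormal shifts from baseline. CK has its own GEE analysis in SAP 8.8.4.

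**The concern.** The category bears on the only adverse-event imbalance that the protocol names from Phase 2. When the sponsor had to interpret that imbalance, it did not use a count of liver-test events. It asked whether ALT rose while GGT stayed normal and CK was high. The Phase 3 plan keeps the count and leaves out the question.

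A patient-incidence row counts each subject once. A subject with a muscle-derived ALT event who later has a GGT event adds nothing further to it. An excess on SA-ER in this row could therefore come from muscle, liver or both. If 5 versus 0 were to recur, the sponsor would have to devise the joint analysis with treatment codes known, which weakens whatever conclusion it reaches about a safety signal.

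**Working it through.** The documents give no event rate, threshold or power figure for liver events, so there is no planned figure to reproduce. The check is a comparison of outputs, followed by two illustrations.

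**1. Content of the list.** 6 transaminase + 2 GGT + 3 non-specific = 11 terms; bilirubin 0, alkaline phosphatase 0.

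**2. What each planned output can show.**

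| Output | Unit | Joint ALT/AST with GGT, bilirubin or CK? |
|---|---|---|
| Liver category (SAP 8.9.1, 10.6.2) | Subjects with any listed event | No |
| Preferred-term tables (SAP 8.9) | Subjects per term | No |
| Laboratory summaries (SAP 8.9) | Subjects per analyte | No |
| CK GEE (SAP 8.8.4) | Mean change in CK | No |

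**3. Why separate laboratory counts do not settle it.** Suppose *a* of *n* subjects in an arm have raised ALT or AST and *g* have raised GGT. The number with both lies between max(0, *a* + *g* − *n*) and min(*a*, *g*). Take *n* = 40 (about 80 subjects randomised 1:1) and, for illustration, *a* = *g* = 5. The lower bound is max(0, 5 + 5 − 40) = 0 and the upper bound is min(5, 5) = 5. The same two table entries fit no subject with both elevations, or every affected subject with both.

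**4. Baseline abnormality.** Exclusion criterion 4 screens out AST or GGT above 3 times the upper limit and names no ALT limit. Some subjects may therefore enter out of range, and for them a normal/abnormal shift cannot register worsening.

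**5. Could a fall in muscle-derived events offset a liver excess?** All rates here are assumed. Let *b* be the placebo rate of muscle-derived events, *r* the relative fall on SA-ER, and *h* the true liver-event rate on SA-ER. Then the SA-ER rate = 1 − (1 − *b*(1 − *r*))(1 − *h*).

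| *b* | *r* | *h* | SA-ER rate | Difference from placebo |
|---|---|---|---|---|
| 20% | 40% | 5% | 1 − 0.88 × 0.95 = 16.4% | −3.6 points |
| 20% | 25% | 5% | 1 − 0.85 × 0.95 = 19.3% | about −0.8 |
| 10% | 30% | 5% | 1 − 0.93 × 0.95 = 11.7% | about +1.7 |
| 5% | 25% | 10% | 1 − 0.9625 × 0.90 = 13.4% | +8.4 |
| 20% | 0% | 5% | 1 − 0.80 × 0.95 = 24.0% | +4.0 |

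Offset is possible with a high background and a large fall, and disappears otherwise. At a 20% rate in both arms, the standard error of the difference is √(2 × 0.20 × 0.80 / 40) = 8.9 points. A 5% liver effect would then be hard to see in the pooled row even with no offset.

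**6. Would the GGT line show something?** If every true liver event were coded to GGT, the chance of at least one among 40 subjects is 1 − (1 − *h*)^40. That is 64% at *h* = 2.5%, 87% at 5% and 98.5% at 10%. The preferred-term tables are therefore informative, but they do not show whether the GGT event accompanied an ALT rise.

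**The case against.** A reader might infer that the category cannot show a liver effect at all. The documents do not support that. GGT is on the list, and it is the marker the protocol itself uses, with CK, to tell liver from muscle. GGT, bilirubin and alkaline phosphatase events would each have a line in the preferred-term tables, and each analyte has its own laboratory summary. Bilirubin and alkaline phosphatase are missing from one supplementary category, not from the safety analysis.

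A reader might also infer that the protocol attributes both ALT and AST to muscle. It does so explicitly only for the Phase 2 ALT elevations; abnormal AST and ALT values are otherwise called sporadic and unrelated to time or arm.

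The most tempting inference is that a fall in muscle injury on SA-ER would hide a liver signal. The protocol does say that "a positive dose-dependent decrease in serum CK levels was observed in the UX001-CL201 Week 24 analysis". In that same study, however, abnormal liver tests ran 5 to 0 against SA-ER, the opposite of masking, and the only placebo count available is 0, in an arm whose size is not given. CK is a tertiary endpoint, and the stated efficacy hypothesis concerns the UEC score, not muscle injury. The share of patients with raised CK is not an adverse-event rate either, because stable chronic elevation is not a new or worsening event.

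All of this stands, and so does the point that a joint table could be built later from individual data. What remains is that no output prespecifies the reading the sponsor has already relied on once.

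**Conclusion.** The point holds as a modest gap in descriptive safety reporting. The category pools muscle-sensitive with more liver-specific terms and omits two analytes that are measured. No planned table shows whether an ALT or AST rise came with GGT, bilirubin or CK. If the Phase 2 imbalance recurs, the planned outputs would show that it exists but could not separate a liver effect from a muscle effect.

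This conclusion rests on the list and the output descriptions alone, not on any assumed event rate. The offset scenario is arithmetically possible but depends wholly on assumed rates and runs against the Phase 2 direction, so it should not be presented as expected. No efficacy test, error rate or sample size is affected.

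**What to change.** 1. In SAP 10.6.2, add the increased and abnormal preferred terms for blood bilirubin and blood alkaline phosphatase. In the 8.9.1 table, show GGT, bilirubin and alkaline phosphatase terms separately from ALT, AST and transaminase terms, and keep the pooled total.

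2. In SAP 8.9, prespecify a by-arm laboratory table. This is a new table of measured values, not a split of the adverse-event category. It would count subjects with ALT or AST above the reference range and above their own baseline, divided into those with and those without GGT or bilirubin above the reference range at the same visit, with CK at that visit alongside. Requiring a rise above baseline deals with subjects who enter already out of range.

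The cost is SAP wording and one or two descriptive tables. ALT, AST, GGT, bilirubin and CK all belong to the chemistry panel drawn at every clinic visit, so no extra sample is needed. The drawback is small cell counts, so the rows should be read descriptively. The change should be made before unblinding.

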## 10.7 Summary of Efficacy Endpoint and Analysis

Test / Instrument	Endpoint	Type of analysis	Time points for Assessment	Statistical approach at week 48/ET analysis
Physical therapy – Hand-held Dynamometry (HHD)	The changes from baseline in Upper Extremity Composite (UEC) Score over time based on bilateral strength recorded in the following muscle groups: gross grip, shoulder abductors, elbow flexors, and elbow extensors	Primary analysis	Weeks 8, 16, 24, 32, 40, and 48	GEE Model
GNEM Functional Activities Scale (GNEM-FAS)	Changes in muscle strength on mobility domain score (reflective of the lower extremities)	Key secondary efficacy analysis	Weeks 8, 16, 24, 32, 40, and 48	GEE Model
Physical therapy – Hand-held Dynamometry (HHD)	The change from baseline in Lower Extremity Composite (LEC) Score over time based on bilateral strength recorded in the following muscle groups: knee flexors, hip flexors, hip extensors, hip abductors and hip adductors.	Key secondary efficacy analysis	Weeks 8, 16, 24, 32, 40, and 48	GEE Model
	Changes in muscle strength in knee extensor over time based on bilateral total force (kg)			
GNEM Functional Activities Scale (GNEM-FAS)	Changes in muscle strength on upper extremity domain score (reflective of the upper extremities)	Other secondary efficacy analysis	Weeks 8, 16, 24, 32, 40, and 48	GEE Model
Sit to Stand	Changes from baseline on the number of times the subject can rise from a seated to a standing position in a 30-second period will be recorded.	Other secondary efficacy analysis	Weeks 8, 16, 24, 32, 40, and 48	GEE Model
Weighed Arm Lift Test	Changes from baseline on the number of times the subject can raise a 1 kg weight above the head in a 30-second period will be recorded.	Other secondary efficacy analysis	Weeks 8, 16, 24, 32, 40, and 48	GEE Model

Test / Instrument	Endpoint	Type of analysis	Time points for Assessment	Statistical approach at week 48/ET analysis
6-Minute Walk Test	Change from baseline in distance walked (meters) during a six minute period.	Other secondary efficacy analysis	Weeks 8, 16, 24, 32, 40, and 48	GEE Model
	Change from baseline in percent predicted of the distance walked (meters) during a six minute period.			
Physical therapy – Hand-held Dynamometry (HHD)	Changes from baseline on Upper Extremity Composite and Lower Extremity Composite Percent Predicted: The percent predicted total force values will be determined based on reference equations adjusting for age, gender, height, and weight.	Tertiary efficacy analysis	Weeks 8, 16, 24, 32, 40, and 48	GEE Model
	Changes from baseline on actual and percent predicted in each Individual Muscle Group: Bilateral total force for each individual muscle group included in the UEC and LEC, and Percent Predicted of knee extensors.		Weeks 8, 16, 24, 32, 40, and 48	GEE Model
GNEM Functional Activities Scale (GNEM-FAS)	Changes from baseline on the total score on the GNEM-FAS	Tertiary efficacy analysis	Weeks 8, 16, 24, 32, 40, and 48	GEE Model
	Changes from baseline on the Self-Care Domain Score on the GNEM-FAS			
Individual Neuromuscular Quality of Life Questionnaire (INQoL)	Changes from baseline on the total score on a 45-item self-report questionnaire on the impact of key muscle disease symptoms on the ability to perform basic activities of daily living, functional independence, relationships and overall well-being	Tertiary efficacy analysis	Weeks 8, 16, 24, 32, 40, and 48	GEE Model
Clinical Global Impression scale (CGI)	The CGI-Severity scale (CGI-S), and improvement (CGI-I) during treatment	Tertiary efficacy analysis	Baseline (CGI-S only), Weeks 24 and 48	GEE Model
	The proportions of patients with reported degrees of change from baseline to week 48			Descriptive statistics
Creatine Kinase	Changes from baseline over time	Tertiary efficacy analysis	Weeks 8, 16, 24, 32, 40, and 48	GEE Model
